8.3.2. Method of Detecting AEs and SAEs

- The method of recording, evaluating, and assessing causality of AEs and SAEs and the procedures for completing and transmitting SAE reports are provided in [Appendix 3](#).
- Care will be taken not to introduce bias when detecting AE and/or SAE. Open-ended and non-leading verbal questioning of the participant is the preferred method to inquire about AE occurrence.

8.3.3. Follow-up of AEs and SAEs

After the initial AE/SAE report, the investigator is required to proactively follow each participant at subsequent visits/contacts. All SAEs, will be followed until the event is resolved, stabilized, otherwise explained, or the participant is lost to follow-up (as defined in Section [7.3](#)). Further information on follow-up procedures is given in [Appendix 3](#).

8.3.4. Regulatory Reporting Requirements for SAEs

- Prompt notification by the investigator to the sponsor of a SAE is essential so that legal obligations and ethical responsibilities towards the safety of participants and the safety of a study intervention under clinical investigation are met.
- The sponsor has a legal responsibility to notify both the local regulatory authority and other regulatory agencies about the safety of a study intervention under clinical investigation. The sponsor will comply with country-specific regulatory requirements relating to safety reporting to the regulatory authority, Institutional Review Boards (IRB)/Independent Ethics Committees (IEC), and investigators.
- Investigator safety reports must be prepared for suspected unexpected serious adverse reactions (SUSAR) according to local regulatory requirements and sponsor policy and forwarded to investigators as necessary.
- An investigator who receives an investigator safety report describing a SAE or other specific safety information e.g., summary or listing of SAE) from the sponsor will review and then file it in the Investigator Site File and will notify the IRB/IEC, if appropriate according to local requirements.

8.3.5. Pregnancy

- Details of all pregnancies in female partners of male participants will be collected after the start of study intervention and until the follow-up visit.
- If a pregnancy is reported, the investigator should inform GSK within 24 hours of learning of the pregnancy and should follow the procedures outlined in [Appendix 4](#).
- Abnormal pregnancy outcomes (e.g., spontaneous abortion, fetal death, stillbirth, congenital anomalies, ectopic pregnancy) are considered SAE.

8.4. Treatment of Overdose

For this study, any dose of AMB (GSK1325760) greater than the protocol defined dose will be considered an overdose.

Due to the mechanism of action, an overdose of AMB could potentially result in hypotension. In case of pronounced hypotension, active cardiovascular support may be required. There are no specific antidotes available for AMB.

In the event of an overdose, the investigator/treating physician should:

1. Contact the Medical Monitor immediately.
2. Closely monitor the participant for AE/SAE and laboratory abnormalities until AMB (GSK1325760) can no longer be detected systemically (at least 3 days).
3. Obtain a plasma sample for PK analysis within 3 days from the date of the last dose of study intervention if requested by the Medical Monitor (determined on a case-by-case basis).
4. Document the quantity of the excess dose as well as the duration of the overdosing in the CRF.

Decisions regarding dose interruptions or modifications will be made by the investigator in consultation with the Medical Monitor based on the clinical evaluation of the participant.

8.5. Pharmacokinetics

8.5.1. Blood Sample Collection

Blood samples for pharmacokinetic (PK) analysis of AMB will be collected at the time points indicated in the SOA (Section 1.3). The actual date and time of each blood sample collection will be recorded.

For analysis of AMB, 2.7 mL of blood will be collected into sodium citrate tubes. Processing, storage and shipping procedures are provided in the SRM.

8.5.2. Sample Analysis

Plasma analysis will be performed under the control of In vitro/In vivo Translation (IVIVT) and Third Party Resource, GlaxoSmithKline. Concentrations of AMB will be determined in plasma samples using the currently approved bioanalytical method. Raw data will be archived at the bioanalytical site (detailed in the SRM).

Once the plasma has been analysed for AMB, any remaining plasma may be analysed for other compound-related metabolites and the results reported under a separate IVIVT, GlaxoSmithKline protocol.

8.6. Palatability Questionnaire

Participants will complete a palatability questionnaire after dosing of AMB tablets dispersed in water. Participants will complete 3 short questions about the smell, taste and feel of the study intervention.

Participants will be shown the questionnaire before dosing, so they know to consider the smell, taste and feel of the study intervention during dosing. Participants will complete the questionnaire within 10 min of dosing. Refer to [Appendix 7](#) for the palatability questionnaire.

8.7. Pharmacodynamics

Pharmacodynamic parameters will not be evaluated in this study.

8.8. Genetics

Genetics will not be evaluated in this study.

8.9. Biomarkers

Biomarkers are not evaluated in this study.

8.10. Health Economics or MEDICAL Resource Utilization and Health Economics

Health Economics/Medical Resource Utilization and Health Economics parameters are not evaluated in this study.

9. STATISTICAL CONSIDERATIONS

9.1. Statistical Hypotheses

No formal hypothesis will be tested. An estimation approach will be used to i) estimate the bioavailability of the test formulation relative to the reference formulation, and ii) for each primary pharmacokinetic endpoint, point estimates and corresponding 90% confidence intervals will be constructed for the ratio of the geometric mean of the test formulation to the geometric mean of the reference formulation.

Success for this study is defined quantitatively as the observed AUC and C_{max} geometric mean ratio of the test formulation to reference formulation falling within 0.6 to 2.5. Both AUC and C_{max} will be used, but AUC (average concentration) is most relevant, because AMB is administered chronically.

The lower and upper limits of success are defined accordingly:

- *Lower limit of success (based on efficacy):* PKPD analysis of adult AMB data (reference formulation) did not show a correlation between exposure and efficacy. However, the lowest approved dose (in Japan), which has shown efficacy is 2.5 mg.

Therefore, we have assumed our lower limit to be the 2.5 mg PK exposure. In relation to the therapeutic dose of 5 mg (to be tested in this study), and assuming linearity (observed in the adult studies), a 0.5-fold change in PK exposure (AUC or C_{max}) for the test formulation relative to the reference formulation, is the lower limit for success.

- *Upper limit of success (based on safety):* In the first time in human study (EE-001), doses up to 15 mg were generally well tolerated (higher doses were associated with an increased frequency of AEs, although there were no SAEs). As the dose to be tested in this study is 5 mg, and 15 mg is considered a tolerated dose, a 3-fold increase in PK exposure (AUC or C_{max}) for the test formulation relative to the reference formulation, is the upper limit for success.

Therefore, the PK exposure (AUC and C_{max}) will be considered both safe and efficacious if the observed geometric mean ratio of test formulation to reference formulation falls within 0.5 to 3.

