1. PROTOCOL SUMMARY

1.1. Synopsis

Protocol Title: An open-label, randomized three period cross-over relative bioavailability study to compare the pharmacokinetic parameters of a lower dose formulation of ambrisentan (GSK1325760) with marketed ambrisentan in healthy adult participants

Short Title: Relative bioavailability study of marketed and lower dose ambrisentan in healthy adult participants

Rationale:

Adult treatments are widely used off label for treatment of pulmonary arterial hypertension (PAH) in children; however, conventional drug delivery methods are not always suitable for younger patients who have difficulties with swallowing conventional tablet formulations. Therefore, the aim is to develop an ambrisentan (AMB) tablet for use in children <8 years, which may be dispersed in water or swallowed (dependent on the age or preference of the child), in order to improve patient compliance and acceptability, whilst maintaining safety and efficacy.

The primary objective of this study is to provide clinically relevant information on the pharmacokinetic (PK) and safety profile of a new lower dose formulation AMB tablet, which is intended for paediatric use. The study will compare the relative bioavailability of the lower dose tablet, dispersed in water and administered orally, with the reference marketed AMB tablet in healthy adults. This study is part of a Paediatric Investigational Plan (PIP) agreed with the European Medicines Agency's Paediatric Committee (PDCO).

Objectives and Endpoints:

Objective	Endpoint
Primary	

 To compare the relative bioavailability of AMB (1 mg x 5 tablets) as tablets dispersed in water or administered orally, with marketed AMB (5 mg x 1 tablet) administered orally, in healthy adult participants under fasted conditions. 	
 Plasma pharmacokinetic parameters of AMB, as data permit: C_{max}, t_{max}, $AUC_{(0-\infty)}$, $AUC_{(0-t)}$ and $t_{1/2}$.

Objective	Endpoint
Secondary	

 To monitor the safety and tolerability of AMB (1 mg x 5 tablets) as tablets dispersed in water or administered orally, compared with marketed AMB (5 mg x 1 tablet) administered orally, in healthy adult participants. 	
 Adverse events (AE), vital signs, electrocardiogram (ECG), and clinical laboratory values

Overall Design:

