4.2. Scientific Rationale for Study Design

This open-label, randomized, cross-over design is well-established for the evaluation of relative bioavailability of different oral dosage forms. Randomization of the treatment sequences is an attempt to prevent bias. No blinding or placebo control will be used, as these are not required for the primary study objective (PK assessment). The washout of 7 days between doses should eliminate the possibility of carryover of drug exposure from the previous dosing period, because AMB $t_{1/2}$ is 17 h.

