9.2.1. Sample Size Assumptions

The sample size assumptions are based on previously reported estimates of within subject CV for AUC $(0-\infty)$ and C_{max} for AMB (study GS-US-300-0112, 2008) [[Volibris](#), 2018].

[Table 3](#) summarizes the estimates of within subject CV for the primary endpoints AUC $(0-\infty)$ and C_{max} .

Table 3 Estimates of within subject CV for the primary endpoints AUC $(0-\infty)$ and C_{max}

CVw: within subject CV	AMB
C_{max}	22%
AUC $(0-\infty)$	15%

The largest of the within subject CV estimates is about 22%, which translate to a standard deviation (SD) of 0.217 on the natural log scale. Based on this SD, the half width of the 90% confidence interval will be 12.5% of the point estimate, approximately 24 subjects will be enrolled to provide at least 20 statistically evaluable subjects.

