9.2.2. Sample Size Sensitivity

Assuming the within subject CV differs from 22% and the number of statistically evaluable subjects is lower than 20, then [Table 4](#) shows the precision (the half width of the 90% confidence interval) for a range of evaluable subjects.

Table 4 Sample Size Sensitivity

Evaluable Subjects	CVw	Precision
20	22%	12.5%
20	34%	19.6%
18	22%	13.2%
18	32%	19.6%
16	22%	14.2%
16	30%	19.6%

Assuming a within subject CV for AUC of 15% (see Section 9.2.1), and with a sample size of 20, if the observed mean AUC ratio of test formulation to reference is 0.6, the probability of the true mean ratio being < 0.5 is $< 0.5\%$. Similarly, if the observed mean AUC ratio of test formulation to reference is 2.5-fold, the probability of the true mean ratio being > 3 is $< 0.5\%$. **So, there is at least 99% probability that the observed AUC will not exceed the boundary of (0.5, 3).**

Assuming a within subject CV for C_{max} of 22% (see Section 9.2.1), and with a sample size of 20, the probability of observing a mean C_{max} ratio of test formulation to reference below 0.5 is $< 2\%$ when the true PK ratio is 0.6. Similarly, if the observed C_{max} ratio of test formulation to reference is 2.5-fold, the probability of the true mean ratio being > 3 -fold is $< 2\%$. **So, there is at least 98% probability that the observed C_{max} will not exceed the boundary of (0.5, 3).**

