9.4. Statistical Analyses

9.4.1. Pharmacokinetic Analyses

Pharmacokinetic analysis will be the responsibility of the Clinical Pharmacokinetics Modelling and Simulation Department, CPKMS, GlaxoSmithKline. Statistical analyses

of the pharmacokinetic parameter data will be the responsibility of Clinical Statistics, GlaxoSmithKline.

Plasma concentration time data for AMB will be analysed by non-compartmental methods with WinNonlin [version 6.3 or above]. Calculations will be based on the actual sampling times recorded during the study although supplementary analysis will be available based on the nominal times. From the plasma concentration-time data, the following pharmacokinetic parameters will be determined, as data permit: maximum observed plasma concentration (C_{max}), time to C_{max} (t_{max}), area under the plasma concentration-time curve [AUC(0-t) and AUC (0- ∞)], and apparent terminal phase half-life ($t_{1/2}$).

The PK parameters, AUC (0- ∞), AUC(0-t), C_{max} , and $t_{1/2}$ will be transformed using natural logarithms. Missing PK parameters will not be imputed. All data from withdrawn subjects will be listed. No adjustment for multiple tests or comparisons is planned.

Pharmacokinetic data will be presented in graphical and/or tabular form and will be summarized descriptively by treatment. Descriptive summary table, graphics, and treatment will also be provided.

Data will be listed and summarized according to GlaxoSmithKline reporting standards, where applicable. Listings will be sorted by subject, period, noting treatment. Summaries will be presented by treatment. Unless stated otherwise, descriptive summaries will include n, mean, standard deviation (SD), coefficient of variation (CV), median, minimum, and maximum for continuous variables, n and percent for categorical variables and geometric mean, 95% confidence interval (CI), and the between-subject CV (CVb) based on geometric mean for the log-transformed PK parameters.

Version 9.3 (or higher) of the SAS system will be used for statistical analysis of the data as well as to generate tables, figures, and listings.

Any deviation(s) from the original analyses planned in the protocol will be reported in the Reporting and Analysis Plan (RAP) and/or in the Clinical Pharmacology Study Report.

All pharmacokinetic data will be stored in the Archives, GlaxoSmithKline Pharmaceuticals R&D.

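### Do the two lists of primary PK endpoints (five parameters in section 3, two in section 9.2.1) leave the main analysis undefined?

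*Protocol*

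**What the plan says.** - **Synopsis (1.1) and section 3.** The primary objective carries five plasma PK parameters: Cmax, tmax, AUC(0-inf), AUC(0-t) and t1/2. They are not ranked.
- **Section 9.2.1.** The sizing text summarises "estimates of within subject CV for the primary endpoints AUC"(0-inf) and Cmax. The title of Table 3 uses the same label for the same pair.
- **Section 9.1.** There is no formal hypothesis test. The plan is that "for each primary pharmacokinetic endpoint, point estimates and corresponding 90% confidence intervals will be constructed for the ratio of the geometric mean", with test in the numerator and reference in the denominator. The endpoints meant are not listed in that sentence. The next paragraph sets the decision rule: "Success for this study is defined quantitatively as the observed AUC and C_{max} geometric mean ratio of the test formulation to reference formulation" must lie within stated limits, and AUC is called the more relevant of the two.
- **Section 9.2.2.** The probability statement for AUC begins "Assuming a within subject CV for AUC of 15% (see Section 9.2.1".
- **Section 9.4.1.** AUC(0-inf), AUC(0-t), Cmax and t1/2 "will be transformed using natural logarithms". tmax is derived but is not in that list. Among the descriptive statistics, the geometric mean and its companions are given "based on geometric mean for the log-transformed PK parameters". No adjustment for multiple comparisons is planned.

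**The concern.** A protocol should have one answer to the question of which endpoints are primary, and this one appears to have two. The point is sharper here than in a trial with a formal test. In an estimation study the set of primary estimates is the main commitment, and section 9.1 ties the ratio and its interval to that set.

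Taken literally, each list causes a difficulty. If section 3 governs, section 9.1 asks for a geometric-mean ratio of tmax, which section 9.4.1 does not prepare for. If section 9.2.1 governs, sections 9.1 and 9.4.1 agree, but the synopsis and section 3 call three parameters primary that are not. The success rule also says AUC without a suffix, although two AUCs stand in the primary row.

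At stake would be which ratios are reported as primary, how tmax is compared between treatments, and whether the sponsor could choose afterwards which AUC decides success.

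**Working it through.** **1. What each list would commit the study to.** There are two comparisons, F1 against R and F2 against R.

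| Reading | Parameters | Ratios |
|---|---|---|
| Section 3 list, literal | 5 | 5 × 2 = 10 |
| Section 3 list, logged parameters only (9.4.1) | 4 | 4 × 2 = 8 |
| Section 9.2.1 list | 2 | 2 × 2 = 4 |
| Ratios used by the success rule, on any reading | 2 | 2 × 2 = 4 |

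The first two rows differ by 10 − 8 = 2 ratios, both of them for tmax. The last row is the same whichever list is adopted.

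**2. Whether a tmax ratio would be produced.** A ratio of geometric means comes from an analysis of logged values. Section 9.4.1 names the four logged parameters, and tmax is not one of them. The same section gives geometric means only for the logged set. Read together, sections 9.1 and 9.4.1 give ratios for at most those four parameters. How tmax is compared, if at all, is ordinary analysis-plan detail.

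**3. Which AUC the success rule means.** Section 9.2.2 takes a within-subject CV of 15% for AUC and refers back to section 9.2.1. Table 3 there gives 15% for AUC(0-inf) and no value for AUC(0-t). The AUC used in the operating characteristics of the success rule is therefore AUC(0-inf).

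**4. Whether the sample size depends on the list.** Inputs from section 9.2.1: CV 22% for Cmax, the larger of the two, and n = 20 evaluable.

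- Log-scale SD = sqrt(ln(1 + 0.22²)) = 0.2174 (protocol: 0.217).
- Standard error of a treatment difference = 0.2174 × sqrt(2/20) = 0.0687.
- Upper half-width of the 90% interval = exp(t × 0.0687) − 1, with t the 95th percentile.
- With 18 degrees of freedom: 12.66%. With 36: 12.31%. With 38: 12.29%. Protocol: 12.5%.

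The stated precision is reproduced. For AUC(0-inf), with CV 15% and SD 0.1492, the same formula gives 8.5% at 18 degrees of freedom, so Cmax drives the size.

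**5. Whether the probability statements in section 9.2.2 depend on the list.** The distance from 0.6 to 0.5, and from 2.5 to 3, is ln(1.2) = 0.1823 on the log scale.

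- AUC: standard error 0.1492 × sqrt(2/20) = 0.0472. The tail probability with 18 degrees of freedom is 0.06%, inside the stated bound of 0.5%.
- Cmax: standard error 0.0687. The tail probability is 0.8%, inside the stated bound of 2%.

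Both use only the AUC(0-inf) and Cmax CVs. The protocol gives no CV for AUC(0-t), t1/2 or tmax, so none of those enters the design figures.

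**The case for a change.** The best case for a change is that primary endpoints are defined in the protocol and not in the analysis plan. An analysis plan that adopts either list will contradict one part of this document. Section 9.2.1 uses the definite article with a closed pair, twice, so it is hard to pass off as a casual phrase. With no test and no alpha, the list is also the only thing that marks a result as primary.

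Part of this stands. The labels do differ, and no sentence reconciles them. Section 9.1, read with section 3 and without section 9.4.1, does reach tmax.

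The rest does not carry weight. A reader who wants to know what decides the study finds it in section 9.1: AUC and Cmax, with AUC foremost. All five parameters are derived and summarised by treatment whichever list is primary, so none is lost from the report. With no alpha to divide, calling AUC(0-t) or t1/2 primary or supportive changes no inference. Section 9.2.1 also admits a milder reading: five parameters serve the primary objective, and two of them have CV estimates and are used for sizing and success. On that reading neither list is wrong.

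**Conclusion.** This is a clerical inconsistency in the use of the word primary, and correcting it would alter no result. The number of ratios labelled primary moves between 10 and 4. The four ratios that decide success, the target of 20 evaluable from about 24, the 12.5% precision and the probability statements in section 9.2.2 are unchanged. The ambiguity over tmax is settled by the list of logged parameters in section 9.4.1, and the ambiguity over AUC by section 9.2.2 with Table 3.

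The conclusion rests on two assumptions: that analysts read section 9.1 together with section 9.4.1, and that the AUC in the success rule is the one whose 15% CV section 9.2.2 uses. Both are the natural readings. A single label would be tidier if the protocol were being amended for another reason, but this point does not call for an amendment.

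### Section 9.1 sets two incompatible success ranges for the same observed ratio, and the wider one (0.5 to 3) leaves no margin at the protocol's own exposure limits

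*Protocol*

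**What the plan says.** Protocol section 9.1 takes an estimation approach: "No formal hypothesis will be tested". For each primary pharmacokinetic endpoint, "point estimates and corresponding 90% confidence intervals will be constructed for the ratio of the geometric mean" of test to reference.

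The section gives success twice, each time on the observed ratio:

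- Near the start: "Success for this study is defined quantitatively as the observed AUC and C_{max} geometric mean ratio" of test to reference within 0.6 to 2.5.
- At the end: exposure is called safe and efficacious "if the observed geometric mean ratio of test formulation to reference formulation falls within 0.5 to 3".

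Between the two it derives the limits. The lower limit is "a 0.5-fold change in PK exposure", from the 2.5 mg dose set against 5 mg. The upper limit is a 3-fold increase, from the tolerated 15 mg dose set against 5 mg. Section 9.1 gives no derivation for 0.6 or 2.5.

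Section 9.2.2 makes the connection. In three of its four probability statements it takes an observed 0.6 or 2.5 and bounds the chance that the true ratio lies beyond 0.5 or 3. The fourth (Cmax, lower side) and the two bold conclusions apply 0.5 and 3 to observed values. Table 4 of that section "shows the precision (the half width of the 90% confidence interval) for a range of evaluable subjects". No section gives the confidence interval a part in the decision.

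**The concern.** A result between the two ranges has no defined verdict. An observed ratio of 0.55 or 2.8 fails by the opening criterion of section 9.1 and is safe and efficacious by the closing one. The reader cannot tell which governs.

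The wider rule is also the weaker one. A limit on exposure concerns the true ratio. If the point estimate only has to reach that limit, a formulation whose true ratio sits exactly on it passes half the time, and the planned 90% interval around a passing estimate can extend well beyond it. At stake is whether the new paediatric tablet is declared to give exposure inside the range that the protocol itself justifies.

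**Working it through.** **Inputs.** Within-subject CV is 22% for Cmax and 15% for AUC(0-∞) (section 9.2.1, Table 3). Evaluable N is 20 (section 9.2), with 16 to 20 in Table 4. Limits are 0.5 and 3, and the alternative range is 0.6 to 2.5 (section 9.1). The protocol does not state the degrees of freedom of the model, so 2N − 4 is used as the main case and N − 1 as a check.

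**Formulas.** SD = √ln(1 + CV²). SE of the log ratio = SD × √(2/N). Half-width factor h = exp(t₀.₉₅ × SE). The 90% interval for an observed ratio r is r/h to r × h.

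**Reproducing the plan.** CV 22% gives SD = 0.2174 (stated 0.217). With N = 20, SE = 0.2174 × √0.1 = 0.0687. The last two columns below give the interval limits at the worst values that pass 0.6 to 2.5.

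| N | CV | Stated half-width | df 2N − 4 | df N − 1 | Lower limit at 0.6 (df N − 1) | Upper limit at 2.5 (df N − 1) |
|---|---|---|---|---|---|---|
| 20 | 22% | 12.5% | 12.3% | 12.6% | 0.533 | 2.816 |
| 20 | 34% | 19.6% | 19.3% | 19.8% | 0.501 | 2.996 |
| 18 | 22% | 13.2% | 13.1% | 13.4% | 0.529 | 2.836 |
| 18 | 32% | 19.6% | 19.3% | 19.9% | 0.501 | 2.996 |
| 16 | 22% | 14.2% | 14.0% | 14.4% | 0.524 | 2.861 |
| 16 | 30% | 19.6% | 19.3% | 20.0% | 0.500 | 2.999 |

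Table 4 reproduces within about 0.4 percentage points. The 9.2.2 bounds also hold. The tail beyond the limit at an observed 0.6 or 2.5 is at most 0.05% for AUC (stated below 0.5%) and 0.4% to 0.8% for Cmax (stated below 2%).

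**What 0.6 to 2.5 does.** 0.6/0.5 = 3/2.5 = 1.2. It is a guard band that works while the 90% half-width is at most 20%. Every Table 4 row meets that, the last only just.

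**What 0.5 to 3 does (Cmax, N = 20, CV 22%, df 36, h = 1.123).** The chance that the true ratio is below 0.5 is the t-distribution function at ln(0.5/r)/SE, the same kind of statement as 9.2.2 makes.

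| Observed ratio | 90% limit nearest the boundary | Chance true ratio < 0.5 | 0.5 to 3 | 0.6 to 2.5 |
|---|---|---|---|---|
| 0.50 | 0.50/1.123 = 0.445 | 50% | pass | fail |
| 0.52 | 0.52/1.123 = 0.463 | 29% | pass | fail |
| 0.55 | 0.55/1.123 = 0.490 | 8.7% | pass | fail |
| 0.60 | 0.60/1.123 = 0.534 | 0.6% | pass | pass |
| 2.90 | 2.90 × 1.123 = 3.26 | n/a | pass | fail |
| 3.00 | 3.00 × 1.123 = 3.37 | n/a | pass | fail |

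The interval stays above 0.5 only if r ≥ 0.5 × 1.123 = 0.562, and below 3 only if r ≤ 3/1.123 = 2.671. Observed Cmax ratios of about 0.50 to 0.56 and 2.67 to 3.0 therefore pass the closing sentence with an interval that crosses a limit. If the true ratio is exactly 0.5 or 3, the chance of passing at that limit is 50% under 0.5 to 3 and 0.4% under 0.6 to 2.5 (normal approximation).

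**What an interval rule would do at plan.** It would pass observed ratios of 0.562 to 2.671 for Cmax. For AUC (CV 15%, h = 1.083) it would pass 0.5 × 1.083 = 0.541 to 3/1.083 = 2.770.

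**The case against.** The best defence is that precision was considered. Section 9.2.2 ties an observed 0.6 or 2.5 to a small chance that the truth lies beyond 0.5 or 3, and tests this at lower N and higher CV. Read with 9.2.2, the 0.6 to 2.5 sentence is a sound pre-specified guard band. The study is declared to be estimation only, and the intervals will be reported, so a wide one would be visible. All of this stands.

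A reader might go further and infer that any rule on the point estimate, including 0.6 to 2.5, lets through results whose interval crosses 0.5 or 3. The documents do not support that within the planned range: in every Table 4 row the interval at 0.6 or 2.5 stays inside the limits, touching them to rounding at worst. The guard band is used up only above a CV of about 34–35% at N = 20 or 30–31% at N = 16, or with fewer than about 9 or 10 contributors at CV 22%. Nothing in the protocol predicts those conditions.

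The defence does not reach the closing sentence of 9.1, which applies 0.5 to 3 to the observed ratio. Nor is that plainly a slip, because the bold conclusions of 9.2.2 also set observed values against 0.5 and 3.

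**Conclusion.** The point holds as a contradiction between two decision rules, one of which has no margin. Under the closing sentence of 9.1, a Cmax ratio of about 0.50 to 0.56 or 2.67 to 3.0 would be called safe and efficacious while the planned 90% interval extends past the protocol's own limit. The chance that the truth lies beyond it is about 50% at the boundary and about 9% at 0.55. The 0.6 to 2.5 sentence does not have this fault under the planning assumptions. Its remaining weakness is that, as a fixed band, it does not adapt if variability turns out well above plan.

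It might also be inferred that an interval rule would give the same verdicts as 0.6 to 2.5 when the plan holds. It would not: it is slightly looser there. An observed Cmax ratio of 0.57 fails 0.6 to 2.5 and passes the interval rule.

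The figures assume a log-scale crossover analysis with SE = SD × √(2/N), 20 participants contributing to each comparison, and the CVs of Table 3. Using N − 1 degrees of freedom changes them very little.

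**What to change.** State one success rule in section 9.1 and say there that 0.5 and 3 are limits for the true ratio. Align the bold conclusions of 9.2.2 with it.

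- **Preferred:** success means that the 90% confidence interval of the geometric mean ratio lies wholly within 0.5 to 3, for AUC(0-∞) and for Cmax, separately for F1/R and F2/R. Remove both rules on the observed ratio.
- **Alternative:** keep the observed ratio within 0.6 to 2.5 and delete the closing sentence that applies 0.5 to 3 to the observed ratio.

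Either is a wording change. The interval is already planned, and no extra data or participants are needed. The preferred rule has a cost to declare: at the planning CVs it passes about 0.56 to 2.67 for Cmax and 0.54 to 2.77 for AUC, so it relaxes the stricter of the two present criteria. It becomes stricter than 0.6 to 2.5 only above a CV of about 34–35% at N = 20, or about 30–31% at N = 16, where the fixed band no longer keeps the interval inside the limits. The alternative avoids that relaxation but does not respond to the precision actually achieved.

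### Section 9.1 applies two different success ranges, 0.6 to 2.5 and 0.5 to 3, to the same observed geometric mean ratio

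*Protocol*

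**What the plan says.** Protocol 9.1 states that no formal hypothesis is tested and that ratios of geometric means will be estimated with 90% confidence intervals. It then sets a quantitative criterion: success is "the observed AUC and C_{max} geometric mean ratio of the test formulation to reference formulation falling within 0.6 to 2.5".

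The next line reads "The lower and upper limits of success are defined accordingly", but the two bullets beneath it give other values. A 0.5-fold change (2.5 mg against 5 mg) "for the test formulation relative to the reference formulation, is the lower limit for success", and a 3-fold increase (15 mg against 5 mg) "for the test formulation relative to the reference formulation, is the upper limit for success". The closing sentence says that exposure "will be considered both safe and efficacious if the observed geometric mean ratio of test formulation to reference formulation falls within 0.5 to 3". No sentence in 9.1 links the two ranges, and nothing there derives 0.6 or 2.5.

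Protocol 9.2.2 uses both ranges in its probability statements for 20 evaluable participants:

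- AUC, lower side: "if the observed mean AUC ratio of test formulation to reference is 0.6, the probability of the true mean ratio being" below 0.5 is put at under 0.5%.
- AUC, upper side: "if the observed mean AUC ratio of test formulation to reference is 2.5-fold, the probability of the true mean ratio being" above 3 is put at under 0.5%.
- Cmax, upper side: "if the observed C_{max} ratio of test formulation to reference is 2.5-fold, the probability of the true mean ratio being" above 3 is put at under 2%.
- Cmax, lower side: the roles are exchanged. The true ratio is 0.6, and the chance of observing less than 0.5 is put at under 2%.

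The two bold conclusions (at least 99% for AUC, at least 98% for Cmax) place the boundary (0.5, 3) on the observed value.

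**The concern.** The same section attaches two ranges to the same statistic under the same word, success. An observed AUC or Cmax ratio in 0.5–0.6 or 2.5–3 fails the first rule and passes the second. The study is open-label and its success criterion rests on point estimates, so the label for such a result could be settled after the data are seen.

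The two ranges also do different work. If 0.6 to 2.5 governs the observed ratio, a pass carries the assurance about the true ratio that most of 9.2.2 describes. If 0.5 to 3 governs it, a pass close to a limit carries no such assurance.

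**Working it through.** **Inputs.** Evaluable n = 20 (9.2). Within-subject CV is 22% for Cmax and 15% for AUC (9.2.1, Table 3). The ranges are those in 9.1. The protocol gives no expected ratio, so the true ratios below are illustrations. Each metric and each test-to-reference comparison is taken singly.

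**Standard errors (log scale).** SDw = √ln(1 + CV²) and SE = SDw × √(2/20).

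- Cmax: SDw = 0.2174 (the protocol gives 0.217), SE = 0.0687.
- AUC: SDw = 0.1492, SE = 0.0472.

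**The protocol's own figures.** The 90% half width for Cmax is exp(t × SE) − 1, which is 12.7% with 18 degrees of freedom and 12.3% with 36. The stated 12.5% lies between them. For 9.2.2, the gap from 0.6 to 0.5 and the gap from 2.5 to 3 are both a factor of 1.2, so the distance is ln(1.2)/SE:

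- AUC: 3.87 SE, tail 0.006% (normal) or 0.02% (t, 36 df), against a stated bound of 0.5%.
- Cmax: 2.65 SE, tail 0.4% or 0.6%, against a stated bound of 2%.

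The stated bounds hold. The fault is not in the arithmetic.

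**Chance of passing each rule.** With lower limit L and upper limit U, P(pass | true ratio) = Φ((ln U − ln true)/SE) − Φ((ln L − ln true)/SE).

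| True ratio | Metric | 0.6 to 2.5 | 0.5 to 3 |
|---|---|---|---|
| 0.55 | Cmax | 10.3% | 91.7% |
| 0.55 | AUC | 3.3% | 97.8% |
| 2.75 | Cmax | 8.3% | 89.7% |
| 2.75 | AUC | 2.2% | 96.7% |

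**How far the disagreement reaches.** The chance that the two rules disagree is the difference between the two pass probabilities.

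| True ratio | Cmax | AUC |
|---|---|---|
| 0.7 | 1.2% | 0.05% |
| 0.8 to 1.5 | below 0.002% | below 0.002% |
| 2.0 | 0.06% | 0.0001% |

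Moving away from 1, disagreement first reaches 1% at 0.70 or 2.13 (Cmax) and at 0.67 or 2.24 (AUC).

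**Assurance about the true ratio.** Three statements in 9.2.2 give a probability for the true ratio once a value is observed, which amounts to a flat prior. On that footing (normal figures, with t on 36 df in brackets):

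| Observed | Question | Cmax | AUC |
|---|---|---|---|
| 0.55 | true < 0.5 | 8.3% (8.7%) | 2.2% (2.5%) |
| 2.75 | true > 3 | 10.3% (10.7%) | 3.3% (3.7%) |
| 0.5 or 3 | beyond that limit | 50% | 50% |

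The observed range that keeps the protocol's own bounds runs from 0.5 × exp(q × SE) to 3 × exp(−q × SE), where q is the t quantile on 36 df. That gives about 0.58 to 2.59 for Cmax at 2%, and about 0.57 to 2.64 for AUC at 0.5%. The range 0.6 to 2.5 lies inside both; 0.5 to 3 does not.

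**The bold conclusions as written.** If the true ratio is 0.6 or 2.5, the observed ratio falls within 0.5 to 3 with probability 99.99% (AUC) or 99.6% (Cmax). They are correct as statements about the observed ratio, but that is not the guard-band statement.

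**The case against.** The intended structure can largely be recovered. Only one sentence in 9.1 says outright what study success is, and it gives 0.6 to 2.5. The closing sentence carries a different label, safe and efficacious. The values 0.5 and 3 come from doses and so read as bounds on exposure, while 0.6 and 2.5 sit exactly a factor of 1.2 inside them, as a guard band would. In 9.2.2 the reversed Cmax statement yields the same number either way (0.40% by the normal calculation), so it may be loose wording and not a rival rule. The sharp contrasts also require a true ratio near 0.55 or 2.75 for the same total dose of the same drug, and no sample size, dosing or stopping decision uses either range.

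Much of this stands. The guard band is the leading reading, the 9.2.2 points follow from the conflict in 9.1, and the practical reach is narrow. The inconsistency itself is not removed: both bullets call 0.5 and 3 limits for success, and the closing sentence of 9.1 says observed. A reader has to infer the rule against explicit text. An analysis plan that adopted either range would still depart from one sentence of the protocol.

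**Conclusion.** The concern holds. Section 9.1 states its only success criterion twice, with different limits on the same observed ratio, and 9.2.2 does not settle which applies. It should be fixed before analysis.

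The effect is confined to observed ratios in 0.5–0.6 and 2.5–3. There it decides the label almost completely; elsewhere it practically never matters. Estimates, confidence intervals, sample size and precision are unaffected.

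The figures rest on 20 evaluable participants, the protocol's CVs, a normal approximation on the log scale and one metric at a time. The joint probability across AUC and Cmax and across the two test presentations was not computed.

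**What to change.** Name one range for the observed ratio and state the role of the other. Which range governs is for the sponsor to decide.

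**If a guard band is intended:**

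1. Keep 0.6 to 2.5 as the only success rule for the observed AUC and Cmax ratios.
2. Relabel 0.5 and 3, in the two bullets and the closing sentence of 9.1, as limits for the true ratio.
3. In 9.2.2, reword the lower Cmax statement so that an observed ratio of 0.6 leaves less than a 2% probability that the true ratio is under 0.5.
4. Reword the bold conclusions so that an observed ratio within 0.6 to 2.5 gives at least 99% (AUC) or 98% (Cmax) probability that the true ratio lies within 0.5 to 3. The stated 0.5% and 2% bounds still hold.

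**If 0.5 to 3 is intended for the observed ratio:**

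1. Change the success definition in the second paragraph of 9.1 to 0.5 to 3.
2. Keep the 99% and 98% figures, but say that they are the chance of observing a ratio within 0.5 to 3 when the true ratio is within 0.6 to 2.5.
3. State that an observed ratio near 0.5 or 3 gives no such assurance about the true ratio.

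The cost is wording in 9.1 and 9.2.2, carried into the analysis plan, with no new data or participants. Under the first option, an observed ratio in 0.5–0.6 or 2.5–3 can no longer be called a success. Under the second, the protocol gives up its stated assurance about the true ratio near the limits.
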